12.0 Study Medication

Fingolimod (FTY720, approved as Gilenya™) a sphingosine-1-phosphate (S1P) receptor modulator and matching placebo tablets will be used as study medication for this study. Placebo tablets will look like fingolimod tablets, with matching shape, taste, and color. Study medication will be purchased directly through the Wishard pharmacy. Wishard pharmacists will over-encapsulate the fingolimod and create matching placebo capsules. Study medication will be stored according to the details on the product label.

Dosing

The dosing used in this study will follow doses recommended for MS which is 0.5 mg by mouth once daily (see package insert for more information).

Compliance

Compliance will be assessed at each visit by direct questioning and medication count of unused medication and packaging to be returned at each visit. Adequate study medication dispensing records will be obtained.

13.0 Concomitant Medication

See Concomitant Medication Table Attachment 2

14.0 Adverse Events

Adverse events (AEs), especially those for which the relationship to study medication is not “unrelated,” will be followed up until they have returned to baseline status or stabilized at the discretion of the principal investigator. If after the follow-up period, return to baseline or stabilization cannot be established an explanation will be recorded in the source documentation.

15.0 Data Safety Monitoring Board

The Indiana University Adult Psychiatry Data Safety Monitoring Board (DSMB) will be responsible for data and safety monitoring. DSMB is responsible for reviewing study procedures, adverse events, safety mailings (if applicable), enrollment, active subjects, and ongoing conduct of the research. The DSMB members can ask questions and make comments and/or recommendations. The IRB is notified of significant findings by way of the DSMB meeting minutes at the time of continuing review. For a list of current DSMB members, see Psychiatry DSMB Board Members supplement. An updated DSMB member list will be provided at the time of Institutional Review Board (IRB) continuing review or upon request.

Due to the small sample size and single site design of this protocol, there is not sufficient justification for conducting interim analyses to examine trends.

Data on the number of subjects enrolled and the number of adverse events will be reviewed by the Board at least **quarterly** and more frequently if needed. The resultant report will be issued to the Indiana University IRB at least at the time of continuing review or more frequently by request.

Any unanticipated events will be immediately directed to the principal investigator who will follow the Indiana University IRB reporting procedures.

16.0 Statistical Considerations

Analyses

In terms of the power to detect a significant effect of this molecule, there are no known calculations with schizophrenia patients. However, an extension phase of a MS registration trial found that patients on fingolimod demonstrated rapid anti-inflammatory responses in relatively small samples (< 35 subjects per dosing arm) (16). In addition, Garver et al (25) examined myelin integrity in schizophrenia and found significant improvement in white matter integrity utilizing a small sample (N=8) of antipsychotic drug responsive schizophrenic patients. Given the above findings, it is reasonable to assume a medium (0.50) to large effect size (0.80) will be observed. Therefore, with a sample size of 40 patients, we could detect a significant effect of treatment (between the fingolimod and placebo groups) with statistical power (37) between .3 and .7, utilizing a two-sided independent test and a significance level of 0.05.

Preliminary analyses will consist of descriptive statistics for all outcome variables, including summary statistics, graphical displays of distributions, and spaghetti plots of individual data over time to detect possible data errors. Demographic and clinical characteristics at baseline will be compared between the two randomized groups, using parametric or nonparametric test statistics as appropriate. Variables that show significant differences will be added to the final models as covariates in order to ensure that the observed treatment effects are not spurious or due to demographic confounds. Data

analysis will be *intent to treat* with all data considered usable providing subjects have completed the randomization visit. To minimize the potential for Type I error, all treatment comparisons will be evaluated based on a two-sided significance level of 0.05. Primary and secondary measures will be examined using ANOVA and ANCOVA general linear modeling analyses for measures resulting in ratio data or the Kruskal-Wallis for those measures that produce ordinal data.

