3.0 Specific Aims

The **primary aims** of this clinical study are to 1) assess the safety of fingolimod in subjects with schizophrenia being treated with antipsychotic drugs, and 2) determine if fingolimod compared to placebo results in symptomatic improvement as measured by reductions in PANSS total score.

Secondary aims include assessment of the effects of fingolimod versus placebo on memory, cognition, positive and negative symptoms, and plasma cytokine levels in addition to gathering preliminary data on the effects of fingolimod on DTI-derived FA and other MRI indices.

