4.0 Study Design

This will be a single site safety and proof of concept study conducted at the Indiana University Psychotic Disorders Program. Forty subjects with schizophrenia or schizoaffective disorders with suboptimally treated symptoms (despite previous and/or current antipsychotic medication exposure) (39) will be randomized 1:1 to double-blind treatment with fingolimod or matched placebo for duration of 8 weeks.

All subjects will be admitted to the Indiana Clinical and Translational Sciences Institute Clinical Research Center (CRC) and remain hospitalized for the first 24 (+/- 2) hours post initial dose of study medication. The CRC is located in Indiana University Hospital and has 24 hour staffing with nurses skilled in conducting Phase 1 and Phase 2 investigational drug studies.

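### Covariates are to be picked by baseline significance tests between randomised arms, and baseline PANSS is not fixed in the primary efficacy model

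*Combined protocol and SAP*

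**What the plan says.** The second primary aim (Section 3.0) is to "determine if fingolimod compared to placebo results in symptomatic improvement as measured by reductions in PANSS total score". The word for the outcome suggests a change score, but no section says whether the analysed response is the change or the final value. Patients "will be randomized 1:1 to double-blind treatment with fingolimod or matched placebo" (Section 4.0), 40 in all.

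Section 16.0 covers covariates in two sentences. First, "Demographic and clinical characteristics at baseline will be compared between the two randomized groups, using parametric or nonparametric test statistics as appropriate". Then, "Variables that show significant differences will be added to the final models as covariates"; the reason given is to guard against spurious or confounded treatment effects. The variables to be tested are not listed. The 0.05 level is set for the treatment comparisons ("all treatment comparisons will be evaluated based on a two-sided significance level of 0.05"); no level is given for the baseline tests.

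On the model itself: "Primary and secondary measures will be examined using ANOVA and ANCOVA general linear modeling analyses for measures resulting in ratio data", with Kruskal-Wallis for ordinal measures. No model terms are named. Attachment 1 schedules PANSS at Visit 2, before the first dose, so a baseline value will exist.

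**The concern.** Under 1:1 randomisation, a significant baseline difference is a chance event. The test therefore measures how unbalanced a variable happens to be, not how strongly it relates to the outcome. Yet it is the relation to outcome that makes a covariate worth having. The rule can bring in irrelevant variables and leave out the one most likely to matter, the baseline value of the primary scale.

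Two things are at stake. The covariates in the primary efficacy contrast are unknown until the data are seen. And precision already paid for may be thrown away in a trial whose own power statement runs only from .3 to .7.

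**Working it through.** **Inputs from Section 16.0.** 40 patients, taken as 20 per arm; standardised effect d = 0.5 to 0.8; two-sided 0.05; stated power .3 to .7. No dropout rate is given, so none is applied.

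**Assumed.** The correlation ρ between baseline and end PANSS is not in the documents; 0.3 to 0.8 is used. Baseline tests are taken at 0.05, and d is expressed in final-score SD units unless noted.

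**Step 1: the plan's own figure.** Two-sample t-test, noncentral t, 38 df, noncentrality d√(20/2): power is 0.338 at d = 0.5 and 0.693 at d = 0.8. This matches the stated .3 to .7 at one decimal. That calculation uses no covariate.

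**Step 2: standard error of the treatment effect, in final-score SD units.**
- Final score, unadjusted: √(2/20) = 0.316
- Change score, unadjusted: √[(2/20)·2(1−ρ)]
- ANCOVA on baseline: √[(2/20)(1−ρ²)(37/36)], where 37/36 allows for estimating the slope

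| ρ | SE change | SE ANCOVA | Variance ratio 2/(1+ρ) × 36/37 | × 40 patients |
|---|---|---|---|---|
| 0.3 | 0.374 | 0.306 | 1.50 | 60 |
| 0.5 | 0.316 | 0.278 | 1.30 | 52 |
| 0.7 | 0.245 | 0.229 | 1.15 | 46 |
| 0.8 | 0.200 | 0.192 | 1.08 | 43 |

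The last column is the number of patients an unadjusted change-score analysis would need to match ANCOVA on 40.

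**Step 3: power under the rule, by simulation.** This is the case most favourable to the rule: only baseline PANSS is tested, and it enters if p < 0.05. It entered in about 5% of runs. Each power cell gives d = 0.5 / d = 0.8, for the change score.

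| ρ | No adjustment | Plan's rule | ANCOVA always | Loss, rule vs ANCOVA (points) |
|---|---|---|---|---|
| 0.3 | 0.26/0.55 | 0.25/0.56 | 0.36/0.72 | 11/16 |
| 0.5 | 0.34/0.69 | 0.34/0.70 | 0.42/0.80 | 8/10 |
| 0.7 | 0.51/0.89 | 0.51/0.89 | 0.57/0.93 | 6/4 |
| 0.8 | 0.68/0.97 | 0.68/0.97 | 0.72/0.98 | 4/1 |

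The rule recovers almost none of what ANCOVA offers.

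**Step 4: sensitivity.**
- *d on the change-score SD:* unadjusted power is 0.34/0.69 at every ρ. ANCOVA gives about 0.47/0.86, 0.42/0.80, 0.38/0.75 and 0.36/0.73 at ρ = 0.3, 0.5, 0.7 and 0.8.
- *Final score as response:* the loss against ANCOVA is about 2–3 points at ρ = 0.3, 8–10 at 0.5, 21–23 at 0.7 and 27–37 at 0.8.
- *Twenty independent variables tested (assumed upper end):* change-score power under the rule falls to 0.22/0.50, 0.30/0.64, 0.47/0.85 and 0.63/0.95.
- *Level of the baseline tests:* with five variables tested at 0.01 or 0.10, baseline PANSS enters in about 1% or 10% of runs. Power at ρ = 0.5 is 0.33/0.69 either way, so the unstated level hardly matters.

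**Step 5: how unpredictable the model is.** The chance that at least one of k independent variables is selected at 0.05 is 1 − 0.95^k: 5% for k = 1, 23% for k = 5, 64% for k = 20.

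**Step 6: type I error.** Under the rule it is 0.03 to 0.05 across the scenarios, so it is not inflated and is sometimes conservative.

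**The case against.** Section 16.0 names ANCOVA, and it speaks of adding unbalanced variables to the final models. That wording is compatible with base models that already adjust for baseline PANSS. If they do, the power loss disappears. This stands as a possible reading, but nothing in the text commits to it; the significance rule is the only stated route for a covariate.

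The quoted rule is also not itself the main source of the loss. With one variable tested, it performs about as well as no adjustment at all; most of the cost comes from not always including baseline PANSS. This is correct. It is a reason to change both sentences together: deleting the rule alone would gain little power.

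Every loss figure depends on a correlation that the documents do not give. Entry requires clinical and antipsychotic stability, so a high value is plausible, and at 0.7 to 0.8 the change-score loss is only 1 to 6 points. That also stands, which is why a range is shown.

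The scenario with 20 independent variables is an upper end. The baseline scales are probably correlated; if the other 19 each correlate 0.6 with PANSS (assumed), the chance of any selection drops from 64% to about 50%.

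Other analyses are conceivable. PANSS total might be treated as ordinal and sent to Kruskal-Wallis, or analysed as repeated measures over its scheduled visits. The plan does not say. This adds to the uncertainty about the primary model.

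Finally, this is a small proof-of-concept study with safety listed first and its limited power disclosed. Even so, PANSS efficacy is also a primary aim, and precision that costs nothing is most useful where power is low.

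**Conclusion.** The concern holds and should be fixed. The plan states a selection rule that does not identify useful covariates, and it nowhere fixes baseline PANSS in the primary efficacy model.

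The change-score loss is moderate at low baseline-to-end correlation and small at high correlation. It would be larger for a final-score analysis when the correlation is high. These sizes rest on the assumed correlation, on 20 analysed patients per arm, and on the significance rule being the only way into the model. The lack of a prespecified set of covariates does not depend on those assumptions. The harm is a data-dependent model and avoidable imprecision, not bias or false positives.

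**What to change.** In Section 16.0:

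- Delete the sentence that selects covariates by significance.
- State that PANSS total is analysed by ANCOVA with treatment and baseline (Visit 2) PANSS total as terms, whatever the baseline comparison shows. With baseline in the model, the treatment estimate is the same for final score and change, so that ambiguity goes too. Naming ANCOVA for PANSS also settles the Kruskal-Wallis question.
- Adjust each other continuous scale for its own baseline value.
- Describe baseline characteristics by arm, but do not use tests on them to choose covariates. Label any adjustment for an observed imbalance as a sensitivity analysis.

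The cost is a wording change and one degree of freedom. No extra patients, visits or data are needed. The primary time point is a separate choice that this change does not settle.

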8.0 Clinical Assessments and Procedures

The following assessments will be administered at one or more visits during the duration of the study according to the study procedures tables (Attachment 1). All assessments will be completed by study personnel based on interviews with the subject or based on questionnaires completed by the subject (i.e. EuroQol).

Diagnostic Interview

The Structured Clinical Interview for DSM-IV-TR (SCID-I/P Patient Edition) will be used to confirm the diagnosis of a psychotic disorder and/or rule out other diagnoses. The SCID-IP is a semi-structured interview designed to evaluate DSM-IV-TR Axis I diagnoses.

The Brief Psychiatric Rating Scale (BPRS)

The BPRS is an 18-item scale measuring positive symptoms, general psychopathology and affective symptoms (38). Some of the items (eg mannerisms and posturing) can be rated simply on observation of the subject; other items (eg anxiety) involve an element of self-reporting by the subject.

Clinical Global Impressions Severity Scale (CGI-S)

The CGI-S will be used for repeated evaluations of global psychopathology (34-35). The CGI-S scale is widely used in schizophrenia research and is a single 7-point Likert scale rating severity of psychopathology on a scale of 1 (normal, not ill) to 7 (very severely ill).

Clinical Global Impressions Severity Improvement Scale (CGI-I)

The CGI-I is used to assess the clinical change as compared to symptoms at baseline using a 7-point Likert scale, ranging from very much improved (1) to very much worse (7) (34-35).

The Positive and Negative Syndrome Scale (PANSS)

The PANSS will be the primary assessment instrument for psychopathology (27). The PANSS contains 30 items that assess symptoms of psychotic disorders including positive, negative and general psychopathology. The PANSS was chosen because of its widespread use in clinical studies of psychosis, and its demonstrated reliability in assessing psychopathology across diverse patient populations.

Personal and Social Performance Scale (PSP)

The PSP scale (32) is a 100-point, single item, clinician rated scale to assess 4 domains of functioning, including personal and social relationships, socially useful activities, self-care and disturbing and aggressive behaviors.

EuroQol Questionnaire-5 dimensions (EQ-5D)

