The Trail Making Test is a neuropsychological test of visual attention and task switching (28). The subject is instructed to connect a set of 25 dots as fast as possible while still maintaining accuracy. The test provides information about visual search speed, scanning, speed of processing, mental flexibility, as well as executive functioning and sensitive to detecting several cognitive impairments. The task requires a subject to 'connect-the-dots' of 25 consecutive targets on a sheet of paper. In Part B version the subject alternates between numbers and letters (1, A, 2, B, etc.) The goal of the test is for the subject is to finish part B as quickly as possible, the time taken to complete the test is used as the primary performance metric. Error rate is not recorded in the paper and pencil version of the test, however, it is assumed that if errors are made it will be reflected in the completion time.

Magnetic Resonance (MR) Measures

The MR work of this project will be conducted at Indiana University Center for Neuroimaging. A Siemens 3T Trio MR system equipped with a novel 32-channel head coil will be used. This study will use an MR imaging protocol optimized for 3T to provide optimal contrast between grey matter, white matter and CSF. The MR imaging protocol is designed to assess brain changes that may be associated with both white matter and grey matter as well as functional changes associated with duration of illness. Subjects will receive a high-resolution, isotropic 1 mm³ T1-weighted gradient echo MRI (MPRAGE) for brain segmentation into gray matter, white matter and cerebrospinal fluid (CSF) and for highly sensitive visualization of T1-signal changes in the brain due to Mn deposition. The diffusion tensor images are collected with a 2mm isotropic resolution to study white matter changes. Functional images will be acquired with T2*-weighted gradient echo-planar imaging (EPI) scans with a resolution of 2.5x2.5x3.5mm to assess brain activity during resting state and task paradigms. Quantitative measurement of cortical thickness and potential atrophy using automated Freesurfer and VBM parcellation methods will be conducted, as well as fronto-temporal axonal tract integrity (cingulum, arcuate and uncinate fasciculi) assessed by DTI tractography; and cortical activation with fMRI coupled with working and semantic memory tasks.

The MRI scanning procedure will last approximately 60 minutes and follows the order described below:

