11.0 Laboratory Assessments

Study associated laboratory assessments (blood and urine) will be collected at time points specified in Study Procedures Table (Attachment 1) and analyzed by a local laboratory with the exception of the urine dipstick assessments which will be collected and analyzed onsite.

A total of 36 mL of blood will be collected for baseline/screening assessments (Visit 1) and 30 mL of blood (at each visit) will be collected at weeks 4 and 8 (Visits 7 and 11).

Laboratory assessments to be completed:

complete blood count with differential (CBC w/diff)
comprehensive metabolic panel (CMP)
magnesium
calcium
lipid panel
hemoglobin A1c (HgbA1c)
thyroid stimulating hormone level (TSH)
pregnancy test (serum (beta HCG) and urine)
varicella zoster titer (VZV titer)
urine toxicology screen
HIV test
hepatitis panel
plasma cytokines

Plasma cytokines

Research staff members will transport the cytokine specimens to Indiana Clinical and Translational Sciences Institute (CTSI) for processing and storage. Specimen handling procedures will be performed based on the CTSI standard operating procedures.

Assay Methodology:

Plasma cytokine and soluble receptor quantifications will be performed in duplicates using pre-validated commercially available assay kits employing Luminex® x-MAP technology. With this approach, we will be able to simultaneously quantify multiple human cytokines of relevance in a single experiment using very small volume of sample (Less than 50- μ l). Each of the assay kits employs 1-2 positive control(s) of known concentration and a negative control in every run. We will follow manufacturer provided established protocols for these assays. The testing panel for cytokines include IFN- γ , IL-10, IL-12p40, IL-12p70, IL-17, IL-1 β , IL-1ra, IL-2, IL-4, IL-6, and TNF- α (Millipore #HCYTOMAG-60K) and the testing panel for soluble receptors include soluble IL-2Ra, soluble IL-6R, soluble TNFRI and soluble TNFRII (Millipore HSCR-32K-04).

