Luminex® is an antibody-based fluorescent immunoassay performed in suspension using distinctly identifiable bead sets. This platform uses internally color-coded microspheres (up to 100 distinct bead sets are available), for coating with a capture antibody specific for a target cytokine. The capability of adding multiple conjugated beads to each sample results in the ability to obtain multiple results from each sample. After the target cytokine from a test sample is captured by the bead, a biotinylated detection antibody is introduced. The reaction mixture is then incubated with Streptavidin-Phycoerythrin conjugate, the reporter molecule, to complete the reaction on the surface of each microsphere. The microspheres are allowed to pass rapidly through a laser which excites the internal dyes marking the microsphere set. A second laser excites PE, the fluorescent dye on the reporter molecule. Finally, high-speed digital-signal processors in the special reader instrument (Bio-Plex 200 system from Bio-Rad) identify each individual microsphere and quantify the result of its bioassay based on fluorescent reporter signals. A cytokine standard mix containing all target cytokines at known calibrated levels will be used to generate separate standard curves for each of the cytokines. Concentrations of each target cytokine will then be estimated using a standard curve specific to that particular cytokine by 5-parameter logistic curve fit method.

Preservation and Specimen Storage:

At the time of specimen submission to and processing by the CTSI the specimens will be stored in the freezers in specially labeled boxes, organized by internal “grids” for easy tracking. The bar-coded ID number and location of each specimen in the freezer will be entered and tracked by the CaTissue specimen database, a CTSI-maintained, password-protected database with limited access. No personal identifiers will appear on the blood tubes stored at the CTSI. The CTSI freezers will be secured and wired to an alarm system. The daily monitoring and maintenance of the freezers will be managed by the CTSI.

All study information will be stored in locked file cabinets and in password-protected computer files. Specimens will be stored by the Indiana CTSI on the IU campus but are not the property of the Indiana CTSI. The PI and IU will remain responsible for the specimens.

All specimens will be kept until they are used in their entirety.

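### The ratio/ordinal rule leaves the test for PANSS total undetermined, and neither reading adjusts by design for the baseline PANSS already collected

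*Combined protocol and SAP*

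**What the plan says.** Section 3.0 sets the efficacy aim: "determine if fingolimod compared to placebo results in symptomatic improvement as measured by reductions in PANSS total score". Section 8.0 describes the instrument: "The PANSS contains 30 items that assess symptoms of psychotic disorders including positive, negative and general psychopathology". Attachment 1 schedules the PANSS at Visit 2 (before dosing), on Days 7 and 28, and at Visit 11 (Day 56).

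Section 16.0 gives one rule for every primary and secondary measure: ANOVA and ANCOVA "for measures resulting in ratio data or the Kruskal-Wallis for those measures that produce ordinal data". It does not sort the measures into these two classes, and neither does any other section. It names no covariate for the ANCOVA, sets no primary time point, and does not choose between final score and change. Its one stated route into the models is the baseline comparison of the arms: "Variables that show significant differences will be added to the final models as covariates".

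Two kinds of secondary measure are plainly on a ratio scale. For Trails B, "the time taken to complete the test is used as the primary performance metric" (Section 8.0). For cytokines, "Concentrations of each target cytokine will then be estimated using a standard curve specific to that particular cytokine" (Section 11.0). No transformation is stated for either.

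**The concern.** The measurement label decides the method, and the primary outcome fits neither label cleanly. A total of 30 rated items has no true ratio property, so on a literal reading only the Kruskal-Wallis branch remains. That test has no place for covariates, so the covariate step in the same section could not be applied to the primary outcome.

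If ratio is loose wording for continuous, PANSS total goes to the linear model. ANOVA and ANCOVA are then both open, and baseline PANSS is not a planned covariate. It would enter only after a significant baseline difference. Under proper randomisation such a difference at the 0.05 level is a chance event in about 1 trial in 20 (assuming that level is also used for the baseline comparisons).

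What is at stake is power, in a trial that states a power of only .3 to .7, and a primary test fixed before the data are seen.

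**Working it through.** **Inputs from Section 16.0 and Section 4.0.** 40 patients randomised 1:1, so n = 20 per arm; effect size d = 0.50 to 0.80; two-sided alpha 0.05; stated power .3 to .7.

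**Assumptions, not in the documents.** Baseline to Day 56 correlation r of 0.5 to 0.7; approximately normal PANSS totals; all 40 patients contribute.

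**Step 1: the plan's own figure.** An unadjusted two-sided two-sample t test (noncentral t, 20 per arm) gives power 0.338 at d = 0.5 and 0.693 at d = 0.8. To one decimal that is .3 and .7, so the stated power reproduces and corresponds to a comparison without baseline adjustment.

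**Step 2: what baseline does to the effect size.** With equal variances at both visits, scaled to 1:

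- Final score: residual variance 1, effective size d.
- Change score: variance 2(1 − r), effective size d / √(2(1 − r)). At r = 0.5 this is d / 1 = d, so change gains nothing. At r = 0.7 it is d / √0.6, which is 0.645 for d = 0.5 and 1.033 for d = 0.8.
- ANCOVA on baseline: residual variance 1 − r², effective size d / √(1 − r²). At r = 0.5 this is d / √0.75, which is 0.577 and 0.924. At r = 0.7 it is d / √0.51, which is 0.700 and 1.120.

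For r between 0 and 1, 1 − r² = (1 − r)(1 + r) is smaller than both 1 and 2(1 − r), so ANCOVA has the smallest residual variance of the three.

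**Step 3: power.** Simulation with 20,000 trials per cell and normal scores rounded to integers, except the ANOVA-on-change row, which is the noncentral t power at the effective sizes in Step 2.

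| Analysis of PANSS total | d=0.5, r=0.5 | d=0.5, r=0.7 | d=0.8, r=0.5 | d=0.8, r=0.7 |
|---|---|---|---|---|
| t test, final score | 0.344 | 0.338 | 0.694 | 0.694 |
| Kruskal-Wallis, final score | 0.327 | 0.321 | 0.670 | 0.671 |
| ANOVA, change | 0.338 | 0.512 | 0.693 | 0.889 |
| Kruskal-Wallis, change | 0.323 | 0.487 | 0.672 | 0.870 |
| ANCOVA on baseline | 0.422 | 0.564 | 0.801 | 0.926 |

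**Step 4: splitting the loss.** On the final score, the rank test costs 0.344 − 0.327 = 0.017 at d = 0.5 and 0.694 − 0.670 = 0.024 at d = 0.8 (r = 0.5): 2 to 3 points at most. Against Kruskal-Wallis on change, ANCOVA gains 0.422 − 0.323 = 0.099 and 0.801 − 0.672 = 0.129 at r = 0.5, and 0.564 − 0.487 = 0.077 and 0.926 − 0.870 = 0.056 at r = 0.7. Against Kruskal-Wallis on the final score at r = 0.7 it gains 0.243 and 0.255. Most of the gain is therefore baseline adjustment.

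**Step 5: type I error.** With no treatment effect, each of the simulated tests rejects in 4.7% to 5.2% of trials.

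**Step 6: ratio-scale secondary measures.** Log-normal outcomes are assumed, with a 0.8 SD shift on the log scale and no baseline adjustment. Power of raw-scale against log-scale ANOVA is 0.641 against 0.694 at log SD 0.5 (5 points), 0.506 against 0.694 at 1.0 (19 points) and 0.342 against 0.695 at 1.5 (35 points). Raw-scale type I error is 0.048, 0.041 and 0.028, so it errs on the conservative side.

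**The case against.** The strongest reply is that Section 16.0, read as a whole, puts PANSS total under the linear model. It speaks of general linear modelling and of final models with covariates, and its power statement reproduces as a t test. Kruskal-Wallis would then be meant for single ratings such as the CGI-S. This is a fair reading, and a reader should not infer that the plan assigns PANSS to Kruskal-Wallis: no section calls it ordinal. But the reading still does not choose between ANOVA and ANCOVA or name baseline PANSS as a covariate.

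Three stronger claims are tempting and do not stand.

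- *That Kruskal-Wallis cannot use baseline.* It can be run on change scores, and the aim's wording about reductions points that way. At r = 0.7 this recovers much of the loss; at r = 0.5 it recovers none. It still takes no covariates.
- *That the rule inflates type I error to about 11%.* That figure (0.106-0.108) needs an analyst who reports the smallest p-value among Kruskal-Wallis on score, Kruskal-Wallis on change, t test and ANCOVA. Choosing only between Kruskal-Wallis and the t test on one endpoint gives 0.056-0.061. Nothing in the plan says such a choice will be made.
- *That cytokines and Trails B times will be analysed raw although skewed.* The documents report no distribution and do not say raw scale. A linear model does not rule out a transformation, although the planned distribution plots are tied only to finding data errors.

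**Conclusion.** The concern holds as a gap in the primary analysis that costs nothing to close. Under either reading of the rule, the plan does not commit to the precision that the Visit 2 PANSS offers. If the correlation is 0.5 to 0.7, a committed baseline-adjusted ANCOVA gains about 8 to 10 points of power over Kruskal-Wallis on change at d = 0.5 and about 6 to 13 points at d = 0.8. Over Kruskal-Wallis on the final score it gains about 10 to 24 and 13 to 26 points.

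The correlation is an assumption; below 0.5 the gain over a final-score analysis shrinks. Dropout would lower all the powers. The measurement label alone accounts for 2 to 3 points, so relabelling PANSS without naming the baseline covariate would recover little. Any single one of these tests, fixed in advance, would be valid. The point on cytokines, soluble receptors and Trails B is secondary, and its size depends entirely on skewness that the documents do not report.

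**What to change.** In Section 16.0, replace the ratio/ordinal sentence for the primary outcome with: PANSS total at Visit 11 (Day 56) is compared between arms by ANCOVA with treatment as factor and Visit 2 PANSS total as a prespecified covariate, whether or not the arms differ at baseline; this is the single primary efficacy test. Kruskal-Wallis is a sensitivity analysis only.

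Then assign each secondary measure to a named method in a short list. Optionally, prespecify for cytokines, soluble receptors and Trails B time an ANCOVA on the log scale with the log baseline value as covariate.

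The cost is a few sentences. No visit, sample or patient is added, because the Visit 2 score is already collected, and one degree of freedom goes to the covariate. Log-scale results would be reported as ratios of geometric means, and cytokine values below the assay limit would need one fixed handling rule.
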